2.7 Potential Benefits of DLI

Although the mechanism by which DLI results in clinical responses is unclear, it is presumed to be a T cell-mediated process. Further analysis of larger numbers of patients is critical to fully understand the mechanisms involved in this response.

Some data suggest that DLI normalizes the T cell receptor (TCR) repertoire and expands the antileukemic cell population. In one study, for example, the TCR repertoire was analyzed before and after DLI among four patients with relapsed chronic myeloid leukemia (CML) and 10 normal controls (25). Initially, the patients' repertoire was characterized by a large number of oligoclonal and clonal patterns, while all controls had a polyclonal pattern. Following infusion of CD4+ lymphocytes, these abnormal patterns slowly normalized over the ensuing several months; by one year, all four patients had an almost normal TCR repertoire. In each patient, expansion of at least one TCR subfamily coincided with the time of disappearance of Philadelphia chromosome-positive cells.

These findings provide evidence of clonal expansion of allogeneic T cells that may be selective mediators of the antileukemic effect. In another study, patients with relapsed CML responding to DLI generated potent antibody responses to CML-associated antigens, suggesting the development of coordinated T and B cell immunity (26).

2.8 Efficacy of DLI

The efficacy of donor lymphocyte infusion (DLI) varies with the underlying malignancy, the dose of infused lymphocytes, and the degree of host lymphodepletion. Outcomes are best for patients with chronic phase chronic myeloid leukemia (CML) followed by patients with lymphoma, multiple myeloma, and acute leukemia (mostly acute myeloid leukemia). Initial studies also suggest that the presence of host-derived regulatory T cells decreases the antitumor effect (28). Patients who respond to DLI will usually demonstrate a clinical response within two to three months, but a full response may take one year or longer(14). Responses can be durable with reports of responses lasting up to 20 years.

Data regarding the efficacy of donor lymphocyte infusions (DLI) come primarily from small case series and two large retrospective studies from Europe and North America:

- The European Group for Blood and Marrow Transplantation reported the results with DLI obtained from 84 patients with chronic myeloid leukemia (CML), 23 with acute myeloid leukemia (AML) and 22 with acute lymphoblastic leukemia (ALL) (29). In this retrospective analysis, 73 percent of patients with relapsed CML had a complete remission after DLI. Remissions, whether defined by molecular or hematologic criteria, were durable. Patients with AML and ALL did not respond as well, as only 29 and zero percent developed a complete remission, respectively. DLI treatment was associated with substantial toxicity: 41 percent developed clinically significant GVHD; 41 percent suffered from myelosuppression; and 13 percent died of causes other than their underlying malignancy.
- A second retrospective analysis (from 25 North American programs) reported the outcomes after DLI in 140 allogeneic transplant patients who relapsed (30). A response rate of 60 percent was observed for patients with CML. The responses were superior in patients with

only cytogenetic relapse or for those treated with DLI while in chronic phase, compared with those who had progressed to either accelerated or blast phases. As in the European study, the results were not as favorable among patients with AML or ALL (15 and 18 percent complete response, respectively). Complications included GVHD (60 percent) and pancytopenia (19 percent).

The decreased response of relapsed acute leukemia to DLI may be due to the more rapid proliferative capacity of malignant cells, since a full response to DLI often requires months. As a result, some clinicians have advocated the use of chemotherapy to first debulk the disease prior to DLI (31). Other clinicians have advocated the use of DLI in patients with acute leukemia and minimal residual disease following HCT (32). As examples:

- In one study, 57 patients with AML, CML, or myelodysplastic syndrome (MDS) relapsing after allogeneic transplant received cytarabine-based chemotherapy, followed by G-CSF-primed DLI without prophylactic immunosuppression (31). Toxicity was appreciable, with a 56 percent incidence of GVHD; treatment-related mortality and two-year overall survival rates were 23 and 19 percent, respectively. Multivariate analysis indicated that those with a post-transplant remission of ·6 months had a relative odds of remission following this treatment approach of 3.7 (95% CI: 1.1-12). Patients with a complete response or no response to this treatment had one-year survival rates of 51 and 5 percent, respectively.
- In another study, 814 patients with standard-risk AML, ALL, or MDS who received allogeneic HCT in first or second complete remission were assessed for minimal residual disease (MRD) to determine eligibility for prophylactic DLI (32). Patients with MRD were eligible for DLI if they had a donor available and had no evidence of active GVHD (56 patients). Patients with MRD who did not have a donor were treated with interleukin-2 (IL-2, 49 patients). When compared with IL-2, DLI resulted in superior rates of disease-free (56 versus 24 percent) and overall (58 versus 28 percent) survival at three years. This compared to rates of disease-free and overall survival at three years of 62 and 66 percent, respectively, in patients with no evidence of MRD after HCT.
- In another study, the combination of azacitidine and donor lymphocyte infusions (DLI) as first salvage therapy for relapse after allogeneic transplantation (allo-HSCT) was studied in 30 patients with acute myeloid leukemia (AML; n=28) or myelodysplastic syndromes (MDS; n=2) within a prospective single-arm multicenter phase-II trial (33). Treatment schedule included eight cycles azacitidine (100 mg/m(2)/day, days 1-5, every 28 days) followed by DLI (from 1-5 × 10(6) to 1-5 × 10(8) CD3(+)cells/kg) after every second azacitidine cycle. A median of three courses azacitidine (range 1-8) were administered, and 22 patients (73%) received DLI. Overall response rate was 30%, including seven complete remissions (CRs, 23%) and two partial remissions (7%). Patients with MDS or AML with myelodysplasia-related changes were more likely to respond (P=0.011), and a lower blast count (P=0.039) as well as high-risk cytogenetics (P=0.035) correlated with the likelihood to achieve CR. Incidence of acute and chronic graft-versus-host disease was 37% and 17%, respectively.

The authors updated their and reported the retrospectively analyzes f 154 patients with acute myeloid leukemia (AML, n = 124), myelodysplastic (MDS, n = 28), or myeloproliferative syndrome (n = 2) (34). All patients received a median number of 4 courses of Aza (range, 4 to 14) and DLI were administered to 105 patients (68%; median number of DLI, 2; range, 1 to 7). Overall survival (OS) at 2 years was $29\% \pm 4\%$. Molecular-only relapse (HR, .14; 95% CI, .03 to .59; P = .007), diagnosis of MDS (HR, .33; 95% CI, .16 to .67; P = .002), and bone marrow blasts <13% (HR, .54; 95% CI, .32 to .91; P = .021) were associated with better OS.

Accordingly, 2-year OS rate was higher in MDS patients ($66\% \pm 10\%$, P = .001) and correlated with disease burden in patients with AML. These results suggested that Aza and DLI were effective and well-tolerated treatment option for patients with relapse after allo-HSCT, in particular those with MDS or AML and low disease burden.

Responses to DLI can be remarkably durable. For example, in an analysis of 66 patients with CML who relapsed and received DLI, 67 percent achieved a molecular complete remission (CR) (35). For those patients achieving a molecular CR, 95 percent were alive and in continuous CR at three years following DLI. Similar results have been reported by others (36-38).

3.0 Patient Eligibility

- 3.1 Inclusion Criteria
 - 3.1.1 Diagnosis of Acute Myeloid Leukemia (AML) and Myelodysplastic Syndrome (including Chronic Myelomonocytic Leukemia [CMML]) according to WHO classification that underwent first allogeneic HSCT with either peripheral blood or bone marrow as the source of the hematopoietic stem cells.
 - 3.1.2 Age 18 to 75 years old.
 - 3.1.3 No more than 1 antigen mismatch at HLA-A, B, C, DRB1 and DQB1 locus for either related or unrelated donor.
 - 3.1.4 High risk AML and MDS patients will be included.
 - 3.1.4.1 Cohort 1: Morphological relapse at least 90 days after stem cell transplant:
 - 3.1.4.1.1 MDS patients: Re-appearance of dysplastic changes in the bone marrow, with or without increase in bone marrow last count, which is pathologically consistent with myelodysplastic syndrome.
 - 3.1.4.1.2 AML patients: Bone marrow blast count >/= 5%.
 - 3.1.4.2 Cohort 2: Persistence or reappearance of minimal residual disease by flow cytometry or cytogenetic or molecular testing while being in morphological remission after allogeneic stem cell transplantation.
 - 3.1.4.3 Cohort 3: High risk AML and MDS patients who are in complete remission morphologically with no evidence of minimal residual disease by flow cytometry or cytogenetic or molecular testing after allogeneic stem cell transplantation.
 - 3.1.4.3.1 MDS patients:
 - 3.1.4.3.1.1 Cytogenetics consistent with poor or very poor risk group by 5-risk classification defined by Schanz, et al (43).
 - 3.1.4.3.1.2 Cytogenetics consistent with monosomal karyotype.
 - 3.1.4.3.1.3 Bone marrow blast count > 5% but less than 20% at any time during their disease course before HSCT.
 - 3.1.4.3.1.4 Peripheral blood blast </=5% at HSCT.
 - 3.1.4.3.1.5 Therapy-related MDS.

3.1.4.3.2 AML patients

3.1.4.3.2.1 Cytogenetics and molecular features consistent with adverse risk group by European LeukemiaNet classification for AML

(see Appendix G.) (22).

- 3.1.4.3.2.2 Presence of minimal residual disease by multi-color flow cytometry or cytogenetics or molecular studies at the time of HSCT.
- 3.1.4.3.2.3 Presence of active disease defined as bone marrow blast count >5% but less than </=10% at the time of HSCT.
- 3.1.4.3.2.4 Peripheral blood blast count </=5% at HSCT.
- 3.1.4.3.2.5 Therapy-related AML.
- 3.1.4.3.3 Be able to start the drug therapy between 42 to 100 days following allogeneic SCT.
 - 3.1.4.3.3.1 No more than 1 prior allogeneic SCT.
 - 3.1.4.3.3.2 Post-transplant bone marrow consistent with complete remission with no evidence of minimal residual disease by flow-cytometry or cytogenetics or molecular testing.
 - 3.1.4.3.3.3 Adequate engraftment within 14 days prior to starting study drug:
 - ANC >/= 1.0 x 10°/L without daily use of myeloid growth factor; and,
 - Platelet >/= 50 x 10°/L without platelet transfusion within 1 week.
- 3.1.5 ECOG performance status of 0, 1, or 2.
- 3.1.6 Serum creatinine </=1.5 mg/dL or creatinine clearance greater or equal than 40 cc/min as defined by the Cockcroft-Gault Equation*.
 - 3.1.6.1 Males (mL/min):(140-age)*IBW(kg) / 72*(serum creatinine(mg/dl))
 - 3.1.6.2 Females (mL/min):0.85*(140-age)*IBW(kg) / 72*(serum creatinine(mg/dl)).
- 3.1.7 Serum bilirubin </= 1.5 x upper limit of normal (ULN).
- 3.1.8 Aspartate transaminase (AST) or alanine transaminase (ALT) </= 2.5 x ULN.
- 3.1.9 Alkaline phosphatase </= 2.5 x UL.
- 3.1.10 No active bleeding.
- 3.1.11 No uncontrolled GVHD.
- 3.1.12 No clinical evidence of life-threatening infection.
- 3.1.13 Capable of understanding the investigational nature, potential risks and benefits of the study, and able to provide valid informed consent.
- 3.1.14 HIV negative and HBs-Ag negative.
- 3.1.15 Negative serum or urine pregnancy test for women with reproductive potential. The only subjects who will be exempt from this criterion are postmenopausal women (defined as women who have been amenorrheic for > 12 months) or subjects who have been surgically sterilized or otherwise proven sterile.

3.2 Exclusion Criteria:

- 3.2.1 Use of any anti-leukemic agents after relapse is documented (note that the use of these anti-leukemic agents given as post-transplant maintenance therapy is allowed in this study, e.g., subcutaneous or oral 5-Azacytidine or FLT3 inhibitors for maintenance) for cohorts 1 and 2.
- 3.2.2 Bone marrow blast count >60% for cohort 1.
- 3.2.3 Use of any of the following after transplantation and prior to starting study therapy for cohort 3.

- 3.2.3.1 Investigational agents/therapies.
- 3.2.3.2 Anti-leukemic agents given as post-transplant maintenance therapy (e.g., subcutaneous or oral 5-Azacytidine or FLT3 inhibitors for maintenance).
- 3.2.3 Active acute GVHD grade II or higher.
- 3.2.4 Active chronic GVHD that is extensive.
- 3.2.5 Concurrent use of systemic immune suppressive other than calcineurin inhibitors and sirolimus.
- 3.2.6 Active uncontrolled systemic fungal, bacterial or viral infection.
- 3.2.7 Symptomatic or uncontrolled arrhythmias.
- 3.2.8 Significant active cardiac disease within the previous 6 months, including:
 - 3.2.8.1 New York Hear Association (NYHA) class III or IV congestive heart failure:
 - 3.2.8.2 Unstable angina or angina requiring surgical or medical intervention, and/or:
 - 3.2.8.3 Myocardial infarction.
- 3.2.9 Known active viral infection with Human Immunodeficiency Virus (HIV), Hepatitis B Virus (HBV) or Hepatitis C Virus (HCV).
- 3.2.10 Prior history of solid tumors other than MDS or AML, unless the subject has been free of the disease for >/= 1 year. However, subjects with the following history/concurrent conditions are allowed:
 - · Basal or squamous cell carcinoma of the skin;
 - Carcinoma in situ of the cervix;
 - Carcinoma in situ of the breast;
 - Incidental histologic finding of prostate cancer (T1a or T1b using the tumor, node, metastasis [TNM] clinical staging system).

- 4.2.1.3 Patients who do not achieve CR/CRi within the first 2 cycles of SGI-110 and still have less than 30% bone marrow bone marrow blasts will continue to receive SGI-110 with an intent to achieve CR.
- 4.2.1.4 Patients who do not achieve CR/CRi within the first 4 cycles of SGI-110 and still have less than 30% bone marrow bone marrow blasts will have the option to receive two more cycles of SGI-110 with an intent to achieve CR if the patient, treating physician and principal investigator determine such an action as the best interest of the patient.
- 4.2.1.5 Patients who do not achieve CR/CRi after the fourth cycle of SGI-110 will be taken off the study if the patient, treating physician and principal investigator do not determine continuation of SGI-110 for 1-2 more cycles with an intent to achieve CR as the best interest of the patient.
- 4.2.1.6 Any patient who does not achieve response after a maximum use of six cycles of SGI-110 will be taken off the study.
- 4.2.1.7 Patients who are reported to achieve CR/CRi at any response assessment time points will continue the study drug, SGI-110, as maintenance therapy at the subsequent treatment cycles.
 - 4.2.1.7.1 The starting maintenance dose will be 40 mg/m2/day (dose level 1) for patients who achieved CR/CRi with doses higher than 40 mg/m2/day.
 - 4.2.1.7.2 The starting maintenance dose will be at least one dose level lower than the treatment dose that led the patient to achieve CR/CRi if the patient was on 40 mg/m2/day dose or less during treatments with active disease.
- 4.2.1.8 Patients will not be taken off therapy with SGI-110 prior to completion of the first 4 courses unless for unequivocal disease progression while on therapy, unacceptable toxicities, or patient request.
- 4.2.1.9 During the treatment cycles given with the intent to achieve CR (patient has active disease), the dose of SGI-110 can be decreased at least by

- one dose level (presented at Section 4.4.4) at the discretion of the treating physician or principal investigator if:
- 4.2.1.9.1 There are grade 3-4 reversible non-hematological toxicities attributable to the drug observed.
- 4.2.1.9.2 Dose change is considered in the best interest of the patient.
- 4.2.1.10 For patients who achieve CR/CRi, treatment with SGI-110 will be continued as maintenance therapy until treatment failure or for a maximum of 12 cycles of SGI-110 treatment.
- 4.2.1.11 Treatment with SGI-110 will be stopped at any time point if patients exhibit evidence of treatment failure, disease progression, experience of unacceptable toxicity, or the investigator determines that the discontinuation of treatment is in the patient's best interest as provided in Section 6.0.
- 4.2.2. Cohort 2: Patients without morphological evidence of relapse but with minimal residual disease.
 - 4.2.2.1 The enrolled patients will start treatment at the dose level 1 which is 40 mg/m2 SC daily, days 1 to 5. Treatment delays up to 70 days are allowed.
 - 4.2.2.2 The response assessments schedule will be as follows:
 - 4.2.2.2.1 The first response assessment will be performed after the second cycle of SGI-110 given prior to initiation of third cycle.
 - 4.2.2.2.2 For patients who have persistency of detectable MRD after the second cycle of SGI-110 and continue to receive SGI-110 the next assessment will be performed after the fourth cycle.
 - 4.2.2.3 For patients who have persistency of detectable MRD after the fourth cycle of SGI-110 and continue to receive SGI-110 the next assessment will be performed after the sixth cycle.
 - 4.2.2.2.4 Patients may have an earlier disease assessment rather than the indicated time point in the study protocol at the discretion of the treating physician and principal investigator.
 - 4.2.2.3 If patients still have detectable MRD even after the fourth cycle of SGI-110, further treatment (maximum two more cycles) with SGI-110 will be given only if the patient, treating physician and principal investigator determine such an action as the best interest of the patient.
 - 4.2.2.4 Patients who are documented to have no detectable MRD at any time point while treated with SGI-110 will continue the study drug as maintenance therapy at subsequent cycles after documentation of MRD negative status.
 - 4.2.2.5 The dose level of SGI-110 can be increased at least one dose level at the discretion of treating physician and principal investigator if persistency of MRD is documented at any time point of disease assessment while on study.
 - 4.2.2.6 For patients with detectable minimal residual disease at study entry, treatment with SGI-110 will be continued until treatment failure or for a

- maximum of 12 cycles if they have become negative for minimal residual disease at any time point within the first 6 cycles of study drug.
- 4.2.2.7 Treatment with SGI-110 will be stopped at any time point if patients exhibit evidence of treatment failure, disease progression, experience of unacceptable toxicity, or the investigator determines that the discontinuation of treatment is in the patient's best interest as provided in Section 6.0.
- 4.2.3. Cohort 3: High risk AML and MDS patients who are in complete remission morphologically with no evidence of minimal residual disease by flow cytometry or cytogenetic or molecular testing after allogeneic stem cell transplantation.
 - 4.2.3.1 The enrolled patients will start treatment at the dose level -1 which is 30 mg/m2 SC daily, days 1 to 5 for each 28-day treatment cycle.
 - 4.2.3.2 Treatment delays up to 70 days will be allowed.
 - 4.2.3.3 The response assessments will be performed per departmental guidelines which is day +100, 6th month, 1- year after allogeneic stem cell transplantation.
 - 4.2.3.4 Disease assessment can be done at any time point after transplantation if it is deemed indicated by the treating physician and/or principal investigator.
 - 4.2.3.5 The dose level of SGI-110 can be increased at least one dose level at the discretion of treating physician and principal investigator if deemed in the best interest of the patient by the treating physician and/or principal investigator.
 - 4.2.3.6 For patients who remain in remission without detectable minimal residual disease at study entry, treatment with SGI-110 will be continued until treatment failure or for a maximum of 12 cycles.
 - 4.2.3.7 Treatment with SGI-110 will be stopped at any time point if patients exhibit evidence of treatment failure, disease progression, experience of unacceptable toxicity, or the treating physician and/or principal investigator determines that the discontinuation of treatment is in the patient's best interest as provided in Section 6.0.
- 4.2.4 **Cross-over.** Patients treated on cohort #2 (patients with minimal residual disease while in morphological remission and cohort #3 (maintenance treatment cohort) will be allowed to receive higher doses of SGI-110 if they progress while on therapy with the study drug. Patients who are considered for cross-over to another study cohort due to progression of disease with an aim to receive higher doses of SGI-110 will be screened for the eligibility of that study cohort prior to initiation of higher doses of study drug.
- 4.3 SGI-110 Reconstitution and Administration

See the current Investigator's Brochure Appendix for details.

4.4. SGI-110 Dose Modifications

Subjects will be monitored for hematologic toxicity and non-hematologic toxicity with the National Cancer Institute (NCI) Common Terminology Criteria Adverse Events (CTCAE, Version 4.0) used as a guide for the grading of the severity.

4.4.1 Hematologic Toxicity

4.4.1.1 Cohort 1:

- 4.4.1.1.1 No dose reductions, delays or modifications are required for hematologic toxicities during the treatment cycles given with an intent to achieve CR/CRi. It is assumed that low counts observed in the presence of active disease (no morphological remission) are due to involvement by the disease and require treatment for improvement. Patients will not require dose modifications for hematological toxicity before they are reported to achieve morphological remission.
- 4.4.1.1.2 For patients who achieve complete morphological remission (CR/CRi) on study, they will receive the subsequent cycles (given as maintenance therapy) approximately every 28 days, provided that their peripheral blood counts have recovered (ANC>=1.0 X 10⁹ /L and platelet count>=50 X 10⁹/L)). If the peripheral count recovery is delayed beyond 42 days from Day 1 of the prior cycle and the delay is presumed to be secondary to therapy (after confirmation of achieving morphological remission), the SGI-110 doses may be reduced at least by one level for subsequent doses (e.g. from 40 to 30 mg).

4.4.1.2 Cohort 2:

- 4.4.1.2.1 No dose reductions, delays or modifications are required for hematologic toxicities during the treatment cycles given in the continuous presence of MRD. It is assumed that low counts in the presence of MRD are due to disease involvement and require treatment for improvement. Indeed, the dose level of SGI-110 can be increased at least one dose level at the discretion of treating physician and principal investigator if persistency of MRD is documented at any time point of disease assessment while on study independent of hematological toxicities observed as indicated at 4.2.2.4.
- 4.4.1.2.2 After the documentation of MRD negative status with the SGI-110 treatment, if the peripheral count recovery is delayed beyond 42 days from Day 1 of the prior cycle and the delay is presumed to be secondary to therapy, the SGI-110 doses may be reduced at least by one level for subsequent doses (e.g., from 30 to 20 mg).
- 4.4.1.3 Cohort 3: If the peripheral count recovery is delayed beyond 42 days from Day 1 of the prior cycle and the delay is presumed to be secondary to therapy, the SGI-110 doses may be reduced at least by one level for subsequent doses (e.g., from 30 to 20 mg).

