2.5 Risks of SGI-110 Based on Early Clinical Data

For the most up-to-date clinical safety information, please refer to the most recent Investigators' Brochure.

The most common risks of SGI-110 are similar to decitabine. These include myelosuppression (neutropenia, febrile neutropenia, thrombocytopenia, and anemia) and its consequences such as fever, infection, sepsis, bacteremia, or bleeding. While in GLP toxicity studies with SGI-110 subcutaneous injections, no adverse local site reactions were noted in the multiple-dose rat and rabbit studies, clinical data indicate injection site pain, irritation, or inflammation in approximately 15% of patients. Local pain seems to be ameliorated by the use of ice packs before or after injection, injecting SGI-110 slowly instead of a push, and carefully avoiding intradermal injections.

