8.0 Adverse Events and Reporting Requirements

8.1 Monitoring, Recording and Reporting of Adverse Events

An AE is any noxious, unintended, or untoward medical occurrence that may appear or worsen in a subject during the course of a study. It may be a new intercurrent illness, a worsening concomitant illness, an injury, or any concomitant impairment of the subject's health, including laboratory test values (as specified by the criteria below), regardless of etiology. Any worsening (ie, any clinically significant adverse change in the frequency or intensity of a pre-existing condition) should be considered an AE. A diagnosis or syndrome should be recorded on the AE page of the eCRF rather than the individual signs or symptoms of the diagnosis or syndrome.

An overdose, accidental or intentional, whether or not it is associated with an AE, or abuse, withdrawal, sensitivity or toxicity to an investigational product (IP) should be reported as an AE. If an overdose is associated with an AE, the overdose and AE should be reported as separate terms.

All subjects will be monitored for AEs during the study. Assessments may include monitoring of any or all of the following parameters: the subject's clinical symptoms, laboratory, pathological, radiological or surgical findings, physical examination findings, or other appropriate tests and procedures.

Related AEs will be recorded by the Investigator from the time the subject signs informed consent to 30 days after the last dose of IP. The Investigator or physician designee is responsible for providing source documentation and assigning attribution for all AEs. Only related adverse events and SAEs will be recorded on the AE page of the eCRF and in the subject's source documents.

Adverse events and protocol specific data will be entered into PDMS/CORe. PDMS/CORe will be used as the electronic case report form for this protocol.

All SAEs must be reported to Astex Drug Safety within 24 hours of the investigator's knowledge of the event by facsimile, or other appropriate method, using the SAE Report Form, or approved equivalent form.

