If an AE is considered serious, both the AE page/screen of the eCRF and the SAE Report Form must be completed.

For each SAE, the Investigator will provide information on severity, start and stop dates, relationship to IP, action taken regarding IP, and outcome.

Recommended Adverse Event Recording Guidelines					
Attribution	Grade 1	Grade 2	Grade 3	Grade 4	Grade 5
			Phase I	Phase I	Phase I
Unrelated	Phase I	Phase I	Phase II	Phase II	Phase II
			i ilase ii	Phase III	Phase III
Unlikely	Phase I	Phase I	Phase I	Phase I	Phase I
				Phase II	Phase II
			Filase II	Phase III	Phase III
	Phase I	Phase I	Phase I	Phase I	Phase I
Possible	Phase II	Phase II	Phase II	Phase II	Phase II
	Filase II	Phase III	Phase III	Phase III	Phase III
	Phase I	Phase I	Phase I	Phase I	Phase I
Probable	Phase II	Phase II	Phase II	Phase II	Phase II
	Phase II	Phase III	Phase III	Phase III	Phase III
	Phase I	Phase I	Phase I	Phase I	Phase I
Definitive	Phase II	Phase II	Phase II	Phase II	Phase II
	FIIdSE II	Phase III	Phase III	Phase III	Phase III

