8.2.3 Causality

The investigator must determine the relationship between the administration of IP and the occurrence of an AE/SAE as Not Suspected or Suspected as defined below:

Not suspected: The temporal relationship of the AE to IP administration makes

a causal relationship unlikely or remote, or other

medications, therapeutic interventions, or underlying conditions provide

a sufficient explanation for the observed event.

Suspected: The temporal relationship of the AE to IP administration makes a

causal relationship possible, and other medications, therapeutic interventions, or underlying conditions do not provide a sufficient

explanation for the observed event.

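### Section 8.1 records only related AEs and SAEs, narrower than safety endpoint 1.3.2.1 and apparently than the recording table in 8.2.1; non-serious grade 3-4 cytopenia is the most exposed event

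*Combined protocol and SAP*

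**What the plan says.** Section 1.3.2.1 makes safety a secondary endpoint. It covers which adverse events occur, how often and how severely, and, as a further item, whether they are tied to SGI-110. It is not confined to related events. Section 7.1 says of the analysis only that such events will be tabulated within each subgroup.

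Section 8.1 narrows what reaches that tabulation: "Only related adverse events and SAEs will be recorded on the AE page of the eCRF". Section 8.3 requires reports of serious events whatever their relationship to the drug, and 8.2.1 requires both an AE page and an SAE form for them.

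Section 8.2.1 also contains a table titled "Recommended Adverse Event Recording Guidelines". It has five attribution levels, from Unrelated to Definitive. Some cells are damaged in the available text, but the Unrelated and Unlikely rows appear to list phase II at grades 3, 4 and 5. Section 8.2.3 uses two levels. The investigator rates the link between drug administration and "the occurrence of an AE/SAE as Not Suspected or Suspected as defined below".

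On cytopenia, section 2.5 says of the drug's most common risks: "These include myelosuppression (neutropenia, febrile neutropenia, thrombocytopenia, and anemia) and its consequences". Section 4.4 states: "Subjects will be monitored for hematologic toxicity and non-hematologic toxicity". For cohort 1 before remission, 4.4.1.1.1 assumes that "low counts observed in the presence of active disease (no morphological remission) are due to involvement by the disease". For cohort 2, 4.4.1.2.1 states: "It is assumed that low counts in the presence of MRD are due to disease involvement and require treatment for improvement". Cohort 2 is defined in 3.1.4.2 by "Persistence or reappearance of minimal residual disease by flow cytometry or cytogenetic or molecular testing while being in morphological remission".

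**The concern.** The endpoint asks for all adverse events with their relationship, while the recording rule filters non-serious events by relationship first. A non-serious grade 3-4 event judged unrelated is then missing from the frequency and severity counts as well as from the related count. The table in 8.2.1 appears to require the opposite, and nothing ranks the two texts.

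The gap applies to every cohort and event type. Cytopenia is the most exposed for two reasons. It is an expected effect of the drug, and the dosing text offers disease as a ready alternative explanation, even for cohort 2, whose patients are in morphological remission. The trial is single-arm, so there is no concurrent rate against which under-recording would show, and attribution is made by investigators who know the treatment. Section 4.4.1.2.1 also permits dose increases while MRD persists, whatever the hematologic toxicity. Those are the cycles in which a complete cytopenia record would be most useful.

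**Working it through.** The plan gives no figure to reproduce, so the check sets the texts side by side and follows one event through them.

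Take a grade 3-4 cytopenia that qualifies as an adverse event but is not serious.

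1. **Is it within the endpoint?** Yes under 1.3.2.1, whatever its relationship to SGI-110.
2. **Does grade make it serious?** No. Under 8.2.7 a laboratory abnormality is an SAE only if it meets a seriousness criterion, regardless of grade.
3. **Can it be rated 'Not suspected'?** Yes under 8.2.3, if timing makes a link unlikely or if something else, including an underlying condition, explains it sufficiently.
4. **Is it then recorded?** That depends on which text governs:

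| Event | Section 8.1 | Table in 8.2.1, phase II |
|---|---|---|
| Serious, grade 3-5, any attribution | Recorded (also 8.3) | Recorded |
| Non-serious grade 3-4, related | Recorded | Recorded |
| Non-serious grade 3-4, judged unrelated | No entry | Appears to be recorded |
| Non-serious grade 1-2, judged unrelated | No entry | No phase II entry |

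The rules part only in the third row.

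**The attribution scales.** An obvious mapping sets Unrelated and Unlikely to 'Not suspected' and the other three levels to 'Suspected'. But 8.2.3 requires two things for 'Suspected': compatible timing, and no other sufficient explanation. A low count soon after dosing, with disease as a rival explanation, could be called Possible on five levels and 'Not suspected' on two. The mapping therefore has to be written down, and so does the meaning of 'related' in 8.1, which is tied to neither scale.

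**Size.** Let N be the number of non-serious grade 3-4 cytopenias that qualify as adverse events, and s the share rated 'Not suspected'. Under 8.1:

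- Entries lost = N × s, and the recorded fraction = 1 − s.
- With s = 0, entries lost = 0. With s = 1, entries lost = N.
- If the table governs, entries lost = 0 for any s.

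The documents give neither N nor s. For context only, section 2.0 reports grade 3-4 hematologic toxicity in 75% of patients in a study of post-transplant decitabine maintenance, and decitabine is the active metabolite of SGI-110. That was a different product and dosing, and the figure is not limited to non-serious events, so it does not supply N. It does suggest that N need not be small.

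**The case against.** The strongest reply is that related-only recording is a deliberate choice, stated twice in 8.1, while the table is headed as a recommendation and is partly unreadable. That stands as a reason for caution about the table. It does not close the gap between 8.1 and an endpoint that is not restricted to related events.

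A reader might infer several stronger things that the documents do not support:

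- **That the protocol tells investigators to attribute low counts to disease.** The sentences in 4.4.1 are dosing rationale. The same text calls the events hematologic toxicities, 4.4 has them monitored and graded, and attribution stays with the investigator under 8.2.3. That section demands a sufficient explanation, and morphological remission argues against disease being one in cohort 2. For cohort 1 in active relapse, disease is a plausible cause of low counts.
- **That the cytopenia data are lost.** Blood counts remain protocol evaluations under 5.1.1. What may be missing is the adverse event entry.
- **That low counts escape the adverse event definition because no dose change is required.** Under 8.2.7, needing treatment or being judged clinically important also qualifies.
- **That severe consequences go unseen.** Serious events are captured regardless of relationship.

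What remains is that a known drug effect can drop out of the recorded non-serious events on an attribution judgment, and that two recording rules are left unreconciled.

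**Conclusion.** The point holds as a minor, cheap improvement. Section 8.1 is narrower than endpoint 1.3.2.1 and appears to conflict with the table in 8.2.1 for non-serious grade 3-4 events judged unrelated. The two attribution scales are not connected. This affects all cohorts, with cytopenia as the leading example.

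The loss is unknown and may be zero. It depends on how many non-serious grade 3-4 cytopenias occur, how often investigators rate them 'Not suspected', and whether sites follow 8.1 or the table. The reading of the table rests on damaged cells; if the original differs, the conflict with the table weakens but the mismatch with the endpoint stays. The primary endpoints for all three cohorts and the stopping rules in section 7 do not use these records and are unaffected.

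**What to change.** 1. Amend 8.1 so that at least grade 3-4 cytopenias are recorded regardless of attribution, or all grade 3-5 events as the table appears to require. State which rule governs, and map the five levels in 8.2.1 to the two in 8.2.3.
2. Add one table of grade 3-4 cytopenia by cohort and cycle, regardless of attribution, from the counts in 5.1.1. Show pre-cycle-1 counts beside it, because only cohort 3 has neutrophil and platelet minimums at entry (3.1.4.3.3.3). The wording of 5.1.1 leaves unclear which mid-cycle counts depend on clinical indication. Clarify this, and report how many counts were available, so that readers can judge whether nadirs were observed.
3. State that the assumptions in 4.4.1.1.1 and 4.4.1.2.1 govern dosing only. The dosing and escalation rules need not change.

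The cost is a short amendment and one table from blood counts the protocol already calls for. Some low counts in the table will be due to disease or present before treatment, and the reported hematologic toxicity rate may rise. Recording all grade 3-5 events adds data entry for unrelated events of every type; the cytopenia-only option avoids that.
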